5 STUDY EVALUATIONS AND MEASUREMENTS

5.1 Screening and Monitoring Evaluations and Measurements

5.1.1 Medical Record Review

The following variables will be abstracted from the medical chart (paper or electronic).

- Name
- Medical record number
- CSN number
- Date/time ED arrival and triage
- Date/time of transfer/discharge from the ED
- Date/time of hospital admission
- Date/time of PICU admission
- Date of birth
- Race
- Ethnicity
- Comorbid medical/surgical conditions
- Pre-hospital medications
- Date, time, and volume of all study fluid administration
- Date, time, and volume of all non-study parenteral fluid administration, including all crystalloids, colloids, blood products, medications, continuous infusions, and flushes
- Total daily recorded volume administered (all “in’s”) and excreted/removed (all “out’s”)
- Date/time of medications/pharmaceuticals administrated during ED and hospitalization
- Laboratory tests (including date/time and results)
- Microbiology tests
- Radiological tests

- Date/time of PICU transfer/discharge
- Date/time of hospital discharge
- Vital status at hospital discharge, study withdrawal, or 90 days following randomization, whichever comes first

5.1.2 Laboratory Evaluations

No routine laboratory evaluations will be required to be performed as part of this study. However, blood levels of lactate, potassium, calcium, sodium, and chloride are routinely measured at presentation and serially over time in pediatric patients with suspected or confirmed septic shock. Any such laboratory evaluations that are performed during the course of routine clinical care in the ED or during the hospitalization may be abstracted from the medical chart.

No laboratory testing will be required in this study beyond that which is performed as part of routine clinical practice. Because both NS and LR are already FDA-approved with demonstrable efficacy and safety for reversing shock and there exists a long history of clinical experience in using both NS and LR in pediatric patients with septic shock, there does not exist sufficient equipoise to justify a clinical trial to investigate either the individual efficacy or safety profile of NS or LR. Rather, this feasibility study is the first step towards a larger, multicenter comparative effectiveness study which will determine the *relative* efficacy and safety of NS versus LR. The relative benefit one fluid over the other was not been proven or even sufficiently tested in large prospective studies and there is, therefore, equipoise for the question of comparative effectiveness. The goal of the comparative effectiveness study will be to determine if there are clinically overt and significant benefits of either NS or LR, relative to each other. We therefore will seek to measure clinically overt and significant efficacy and safety outcomes which would be identified as part of routine clinical practice rather than specifying biochemical laboratory tests that may identify values outside the range of normal but would not otherwise be considered “clinically overt and significant”. For example, there is no compelling reason to shift clinical practice from predominant NS resuscitation to predominant LR resuscitation solely because of hyperchloremia *if* this biochemical abnormality does not translate into a “clinically overt and significant” patient outcome. For these reasons, no laboratory testing will be required beyond that which is performed as part of routine clinical practice. However, as described in Section 6.3.4, for the purposes of this feasibility study, we will track laboratory testing performed as part of routine clinical practice in order to determine the frequency that laboratory results are available for the specified safety outcome measures listed in Section 5.4. In addition, if the designated “stopping criteria” listed in Section 4.6.1 are identified during the course of routine, clinician-directed physical and/or laboratory assessment, no further study fluid will be recommended.

5.1.3 Radiographic Evaluations

No routine radiographic evaluations will be required as part of this study. However, radiographic studies that are performed during the course of routine clinical care will be

abstracted from the medical chart as needed to determine site of infection, diagnosis of venothromboembolism, and diagnosis of cerebral edema/intracranial hypertension.

5.2 Feasibility Evaluations

5.2.1 Aim 1

The primary outcome for Aim 1 will be the proportion of total crystalloids administered as saline in each arm, and the secondary outcome will be the proportion of total crystalloids administered as non-study fluid (i.e., cross-over) in each arm.

The primary outcome will be measured in each subject by dividing the total volume (in mL) of NS administered as fluid boluses or continuous IV/IO fluids (numerator) by the total volume (in mL) of all crystalloids (NS, LR, and Plasma-lyte [with or without dextrose and/or other electrolyte additives]) administered as fluid boluses or continuous IV/IO fluids during the intervention phase (denominator). NS or LR (or other crystalloid) administered to “flush” a medication or check line patency, as a “carrier” fluid designed to maintain IV/IO patency or assist delivery of another medication, or used solely as a diluent for another medication will be excluded from both the numerator and denominator.

The secondary outcome will be measured in each subject by dividing the total volume (in mL) of non-study fluid given as either NS (for patients randomized to the LR arm) or LR (for patients randomized to the NS arm), including pre-study enrollment crystalloid fluids (numerator), by the total volume (in mL) of NS plus LR [with or without dextrose and/or other electrolyte additives]) administered as fluid boluses or continuous IV/IO fluids during the intervention phase (denominator). NS or LR (or other crystalloid) administered to “flush” a medication or check line patency, as a “carrier” fluid designed to maintain IV/IO patency or assist delivery of another medication, or used solely as a diluent for another medication will be excluded from both the numerator and denominator.

5.2.2 Aim 2

The outcome for Aim 2 will be the proportion of eligible patients treated in the CHOP ED who are enrolled, randomized, and treated with study fluid. This outcome will be measured by dividing the number of eligible patients treated in the CHOP ED who are enrolled, randomized, and treated with study fluid (numerator) by the total number of eligible patients treated in the CHOP ED (denominator) over the entire enrollment period of the study.

5.2.3 Aim 3

The outcomes for Aim 3 will be the proportion of eligible patients who meet criteria for EFIC who are not enrolled, randomized, and treated with study fluid or, if enrolled, withdraw prior to completion of the follow-up phase. This outcome will be measured by dividing the number of patients eligible but not enrolled through EFIC and/or withdraw prior to completion of the follow-up phase (numerator) by the number of eligible patients who meet criteria for EFIC (denominator) over the entire enrollment period of the study.

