3.1.2 Intervention Phase

The intervention to be tested is fluid resuscitation with LR compared to the “usual practice” control fluid of NS. Other than prescribing which crystalloid fluid to use, the intervention will be purposely implemented without intense efforts to standardize timing and volume of fluid resuscitation or other components of clinical care.

The proposed interventional plan is that, prior to receipt of >40 mL/kg of crystalloid bolus fluid, eligible patients will be randomized to receive either NS or LR for all remaining fluid administration (bolus and maintenance) for up to 48 hours. The study period will end at 11:59pm on the calendar day following randomization such that all patients receive at least 24 hours of study fluid, which is the time-window from presentation in which most fluid resuscitation is completed for septic shock.²⁷ This time point for terminating the intervention phase was selected because it provided a pragmatic endpoint that can be used by clinicians to signal the point at which to cease study fluid administration. Selective fluid administration has been previously shown to result in widely different amounts of saline use,⁴⁷ though application of these findings in adults using a different allocation strategy to the one proposed for our study is not clear. Study fluids will not be blinded due to costs and interventions that are not in keeping with a simple, pragmatic trial and based on results from the previously published SPLIT fluid trial in which two-thirds of clinicians correctly

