4.4 Concomitant Medication

All prior and concomitant use of antibiotics, acyclovir, corticosteroids, bicarbonate, parenteral calcium, blood products, crystalloid and colloid fluids (including hypertonic saline), mannitol, intravenous immunoglobulin, diuretics, non-steroidal anti-inflammatory medications (NSAIDS), unfractionated or low-molecular weight heparin, vasoactive infusions (i.e., dopamine, dobutamine, epinephrine, norepinephrine, phenylephrine, milrinone, vasopressin) within one day prior to the screening visit and through the end of the study will be recorded. The dates of administration, dosage, and reason for use will be included.

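### The Aim 1 compliance ratios count only listed fluids, so any other crystalloid given in the window would drop out of the feasibility decision

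*Combined protocol and SAP*

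**What the plan says.** Section 3.1.2 has patients "randomized to receive either NS or LR for all remaining fluid administration (bolus and maintenance) for up to 48 hours", and Section 3.2 extends the assigned fluid to all later crystalloid in the study window.

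Section 5.2.1 computes the primary outcome for each subject by "dividing the total volume (in mL) of NS administered as fluid boluses or continuous IV/IO fluids (numerator") and then "by the total volume (in mL) of all crystalloids (NS, LR, and Plasma-lyte"), each with or without additives. The numerator is NS in both arms. Flushes, carriers and diluents are left out of both parts.

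The secondary (cross-over) outcome is labelled a proportion of total crystalloids in Sections 5.2.1, 6.2 and 6.3.2. Its formula divides the volume of the opposite trial fluid "by the total volume (in mL) of NS plus LR".

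Section 6.3.2 declares feasibility if either of two criteria is met. Criterion 1 is a difference in mean NS use of at least 65 points with a lower 95% limit above 60. Criterion 2 requires at least 85% of NS-arm subjects to have 90% or more of *study fluid* as NS, and at least 80% of LR-arm subjects to have 75% or more as LR. The denominator of criterion 2 is not defined.

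Other fluids are recorded. Section 5.1.1 abstracts "Date, time, and volume of all non-study parenteral fluid administration, including all crystalloids, colloids, blood products, medications, continuous infusions, and flushes", and Section 4.4 records "crystalloid and colloid fluids (including hypertonic saline").

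**The concern.** Compliance is the primary objective, and it is defined against an assignment that covers bolus and maintenance fluid alike. A base crystalloid other than NS or LR is therefore not the assigned treatment, whether it was given by preference or because study fluid was stopped as Sections 3.1.2 and 4.6.1 allow. Those subjects stay in the analysis, and their fluids continue to be recorded.

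Under the formulas as written, such volume enters neither numerator nor denominator unless it is Plasma-Lyte, and Plasma-Lyte counts only in the primary ratio. A child whose maintenance ran on an unlisted crystalloid would be scored on the remaining fluid alone. A randomized child given only unlisted crystalloid would have the ratio 0/0, although Section 6.3.2 includes all randomized subjects. Because either criterion is enough, a flattering result on criterion 2 alone could support going on to the multicenter trial.

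**Working it through.** **Inputs.** The formulas are from Section 5.2.1 and the criteria and the 90% versus 25% example from Section 6.3.2. Section 6.4 gives the planning means (96% and 91% correct fluid) and 35 subjects per arm. The share h of unlisted crystalloid is not in the documents, so it is varied.

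**1. The plan's own example.** 90 − 25 = 65 points, which reproduces.

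**2. One subject.** Let N, L, P and O be the volumes of NS, LR, Plasma-Lyte and other crystalloid, and h = O/(N+L+P+O). The plan uses N/(N+L+P); over all crystalloid it is N/(N+L+P+O). The plan's share is thus the all-crystalloid share times 1/(1−h). The same holds for the LR share taken over the listed fluids. Volumes below are illustrative, with no pre-enrollment fluid counted.

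- NS arm, 1000 mL NS + 500 mL other: the plan gives 1000/1000 = 100%; over all crystalloid, 1000/1500 = 66.7%.
- LR arm, 900 mL LR + 100 mL NS + 500 mL other: the LR share is 900/1000 = 90% against 900/1500 = 60%. The NS share, which is the primary metric, is 100/1000 = 10% against 100/1500 = 6.7%. Cross-over is 10% as defined, against (100 + 500)/1500 = 40% if all non-assigned crystalloid counts. The plan's bar for the arm mean is 25%.

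**3. Criterion 2.** With 35 per arm, the bars are 30 subjects (0.85 × 35 = 29.75) and 28 subjects (0.80 × 35 = 28). A child with only the assigned fluid among listed fluids scores 100% on them and 1 − h over all crystalloid. The child is wrongly counted as a success when 1 − h < 0.90, so h > 10% (NS arm), or 1 − h < 0.75, so h > 25% (LR arm). As an assumed case, let 7 of 35 NS-arm children exceed 10% and the rest comply fully. The listed-fluid ratio counts 35/35; over all crystalloid it is 28/35 = 80%, below the 85% bar.

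**4. Criterion 1.** Take NS use of 96% and 9%, assuming that all non-LR fluid in the LR arm is NS. The plan's formula reports 87.0 points. With h uniform within an arm, the difference over all crystalloid is 87(1−h) if h applies to both arms, 96(1−h) − 9 if to the NS arm only, and 96 − 9(1−h) if to the LR arm only.

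| h | Both arms | NS arm only | LR arm only |
|---|---|---|---|
| 10% | 78.3 | 77.4 | 87.9 |
| 20% | 69.6 | 67.8 | 88.8 |
| 25% | 65.25 | 63.0 | 89.25 |
| 30% | 60.9 | 58.2 | 89.7 |

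The 65-point bar is crossed at h = 1 − 65/87 = 25.3% (both arms) or h = 1 − 74/96 = 22.9% (NS arm only). When h is confined to the LR arm, the plan understates the separation.

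Starting from the plan's 90% versus 25% example, h = 10% gives 65 × 0.9 = 58.5 (both arms), 81 − 25 = 56.0 (NS arm only), or 90 − 22.5 = 67.5 (LR arm only).

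These are point estimates. The separate requirement on the lower confidence limit could fail sooner, but the documents do not give the spread needed to show it.

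**5. Power.** The stated power of about 80% for criterion 2 does not bear on this point. For the record, exact binomial tails at the printed rates of 0.90 and 0.89 give 0.868 × 0.967 = 0.840. However, 0.90 is the NS-arm rate at an 85% cut, and the criterion uses 90%. At 0.89 for the NS arm the product is 0.791, so the stated figure is plausible but cannot be confirmed.

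**The case against.** The strongest reply is that *all crystalloids* governs and the bracketed list only illustrates it. Section 2.1 and the example in Section 6.3.2 speak of crystalloid without restriction, and the flush exclusion in Section 5.2.1 mentions other crystalloid. That makes the primary formula ambiguous rather than plainly wrong. It does not rescue the cross-over formula, which names two fluids under a total-crystalloid label, or criterion 2, which names no denominator.

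A second reply is that Section 3.1.2 treats cross-over as receiving the opposite trial fluid, which NS plus LR suits. That is fair for the construct, but the endpoint is then mislabelled and no secondary measure captures other departures.

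Third, widening the denominator lowers the NS share in the LR arm, so an LR-arm departure would look like better separation on criterion 1. This is correct. It is why the cross-over numerator and criterion 2 must change along with the primary denominator.

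A reader might also infer stronger claims that the documents do not support:

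- *That such fluid is invisible to the trial.* It is not; Section 5.1.1 abstracts the volumes, and the ratios can be recomputed.
- *That half-normal saline or dextrose-only maintenance is common here.* Half-normal saline appears only as an arm of the diabetic ketoacidosis trial in Section 6.4. The dextrose preparations that Section 1.4 calls common are NS- or LR-based and are counted.
- *That the NS-arm figure in criterion 2 is 100% by definition.* This follows only if study fluid means the assigned fluid. Sections 3.1.2 and 9.1.2 use the term for both products, which would make the ratio NS/(NS+LR).

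**Conclusion.** The point holds in conditional form. The three Aim 1 measures do not share a denominator, and read literally none of them counts every crystalloid that the assignment covers. If unlisted crystalloid is used, each arm's correct-fluid share is overstated by 1/(1−h), taking h as uniform within the arm. Criterion 2 is the more sensitive: 10% of a child's volume is enough to misclassify in the NS arm and 25% in the LR arm. Criterion 1 is more robust at the planning means, where equal use in both arms must exceed about 25% of volume before the bar is wrongly met. It is fragile near the bar, as the 58.5-point result shows.

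It would go too far to say that compliance is overstated, or that the error always favors a positive decision. No usage rate is given, and the criterion 1 difference is understated when the other fluid is confined to the LR arm (87.0 reported against 88.8 at h = 20%). The definitions should be settled before the data are analyzed.

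**What to change.** Use one denominator for the primary ratio, the cross-over ratio and criterion 2: all IV/IO crystalloid of any composition given as bolus or continuous fluid during the intervention phase, keeping the flush, carrier and diluent exclusions. As worded this would include hypertonic saline; if that is not intended, say so by name.

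In the cross-over numerator, count any non-assigned crystalloid given in the window. The present numerator also includes pre-enrollment fluid, which lies outside this denominator and is a separate matter to settle. In criterion 2, replace *of study fluid* with *of total crystalloid*. Report the current definitions as a sensitivity analysis.

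This removes the 0/0 case for a child given only unlisted crystalloid. A child given no crystalloid at all in the window would still need a stated rule.

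The cost is wording and a small amount of programming. The volumes are already abstracted, and the sample size need not change on this ground. Reported compliance may be somewhat lower.

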1.4 Selection of Drugs and Dosages

Both NS and LR are available with identical storage volumes and dosing strategies.

For this study, standard storage units of NS and LR will be used, including 250, 500, and 1,000 mL units. At the discretion of the care team, dextrose may be added to either NS or LR for resuscitation (uncommon) or maintenance (common) fluid therapy. Commonly used dextrose preparations for pediatric septic shock include NS or LR with 5% or 10% dextrose which are also available in standard volumes of 250, 500, and 1,000 mL units. Potassium or other electrolytes may be added to either NS or LR as clinically indicated.

Volume for fluid resuscitation is typically 10-20 mL/kg per dose administered over 5-20 minutes via the intravenous or intraosseous route, though children with sepsis often receive >100-200 mL/kg total crystalloid volume resuscitation within 24-48 hours. Volume for maintenance fluids is typically determined by patient weight, assessment of intravascular volume status, and need for a specific glucose infusion rate. However, for this study, only the type of base fluid (i.e., NS or LR) will be determined by study protocol, while the actual volume administered (per bolus dose, per hour, and in total), duration of administration, and need for electrolyte additives (i.e., dextrose, potassium, others) will be at the complete discretion of the treating care team.

The costs for NS and LR are equivalent, with both fluids at approximately \$1-2.00 per liter. Since the volume of fluid will be determined by the care team and use of both NS and LR are consistent with published guidelines for crystalloid resuscitation of pediatric septic shock, the randomized selection of fluid will not significantly alter health care costs for subjects enrolled in this study.

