2.1 Primary Objective (or Aim)

The primary objective of this study is to determine compliance with study fluid administration, throughout the intervention phase, within each randomized arm using a pragmatic study design.

Specifically, we will determine if the proposed study design is feasible to provide a clinically important difference in crystalloid fluid type between the two study arms by measuring the proportion of intravenous crystalloid fluid administered as 0.9% saline for pediatric patients with suspected septic shock randomized to fluid resuscitation with either saline or lactated Ringer's.

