sepsis/septic within 24 hours of ED presentation were missed.⁴⁸ However, because the positive predictive value of this combined approach was 25.4%, we have required the additional inclusion criterion of administration of at least 20 mL/kg IV/IO fluid resuscitation with additional fluid deemed likely to be necessary to treat poor perfusion, defined as either hypotension or abnormal (either “flash” or >3 second) capillary refill (as determined by clinician’s judgment).

- 3) Administration of at least 20 mL/kg IV/IO fluid resuscitation
- 4) Receipt of ≤ 40 mL/kg IV/IO crystalloid fluid prior to randomization
- 5) Additional fluid deemed likely to be necessary to treat poor perfusion, defined as either hypotension or abnormal (either “flash” or >2 second) capillary refill (as determined by clinician’s judgment)¹⁰

NOTE: Due to the pragmatic nature of this study that is designed to reflect usual clinical practice, we will not define specific thresholds for either hypotension or abnormal capillary refill but rather defer to the treating clinician’s discretion to determine hypotension and abnormal capillary refill.

- 6) Parental/guardian permission (informed consent) if time permits; otherwise, EFIC criteria met

NOTE: For patients who may be transferred to the CHOP ED from an outside facility, many will have started fluid resuscitation prior to arrival in the CHOP ED. If volume of crystalloid fluid administration cannot be easily determined such that receipt of ≤ 40 mL/kg IV/IO crystalloid volume cannot be easily verified, these patients will be operationalized as not meeting the ≤ 40 mL/kg inclusion criterion.

NOTE: Patients who are randomized to a study arm at ≤ 40 mL/kg crystalloid fluid resuscitation *but for whom study fluid is not initiated until after >40 mL/kg* will still be included and should commence with administration of study fluid for the duration of the remaining intervention phase.

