4.2 Intervention Phase

The intervention phase will start immediately following the patient's first 20 mL/kg and randomization has been determined, and will end at 11:59 pm on the calendar day following randomization. During this period, the follow study procedures will occur:

- Dispense study fluid
- Monitor study fluid adherence
- If enrollment after EFIC, review inclusion/exclusion criteria
- If enrollment after EFIC, inform subject and LAR of study enrollment (as soon as feasibly possible)
- Medical record review
- Adverse event reporting

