6 STATISTICAL CONSIDERATIONS

6.1 Primary Endpoint

The primary endpoint will be the proportion of total crystalloids administered as saline in each arm during the intervention phase (Aim 1).

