- 2) The current ACCM guidelines to treat hemodynamic shock in pediatric sepsis recommend crystalloid fluid resuscitation within 15 minutes of recognition of septic shock. Thus, in most instances, this exceedingly short time window is too short for a proper discussion of prospective informed consent, including sufficient opportunity to explain study procedures, discuss risks/benefits, and answer all questions, to be feasible. Expanding the therapeutic window beyond 15 minutes would result in either 1) delay of fluid resuscitation which would place patients at risk of life-threatening complications of untreated septic shock, including cardiac arrest and death and/or 2) administration of a large volume of pre-study, non-randomized fluids that will prevent the necessary clinically important separation between study arms to determine comparative effectiveness of NS versus LR resuscitation. Our data from CHOP and two additional published studies demonstrate that 25-55% of deaths due to pediatric septic shock occur within 24 hours of presentation, necessitating rapid screening, enrollment, and randomization if we are to maximize the chances of identifying a benefit for one resuscitation strategy versus another. In addition, because of the pragmatic study design, front-line clinicians will be required to screen and enroll eligible patients. Given the life-threatening nature of septic shock and need for prompt resuscitation, removing a member of the clinical care team to seek prospective informed consent may compromise clinical care and place patients at risk of life-threatening complications of untreated septic shock, including cardiac arrest and death. Finally, our data from a survey conducted in the CHOP ED, supports that parents/guardians would prefer not to be approached for informed consent in the initial critical period of their child's emergency care. Therefore, in most instances, obtaining informed consent will not be feasible.

In rare circumstances, fluid resuscitation may be necessarily delayed such as with parental or clinician initial preference to avoid or limit fluid resuscitation (e.g., concern for concurrent heart failure for which large-volume, rapid fluid resuscitation may not be in the best interest of the patient) or with delayed IV/IO access. In these rare circumstances when the therapeutic window is extended beyond 15 minutes from recognition of septic shock, there may be an opportunity to seek prospective informed consent.

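### The primary saline share measures compliance after randomization but not the total difference in fluid type between arms, and the one ratio that counts earlier fluid has mismatched periods

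*Combined protocol and SAP*

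**What the plan says.** Section 2.1 gives the primary objective in two sentences. The first is compliance with study fluid over the intervention phase within each arm. The second says the trial will "determine if the proposed study design is feasible to provide a clinically important difference in crystalloid fluid type between the two study arms", measured by the share of crystalloid given as NS.

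Section 5.2.1 sets the denominator of that share as crystalloid "administered as fluid boluses or continuous IV/IO fluids during the intervention phase (denominator"). It gives the numerator no explicit window, but section 6.1 settles this by defining the endpoint as the "proportion of total crystalloids administered as saline in each arm during the intervention phase (Aim 1"). Section 4.2 starts the phase after the "first 20 mL/kg and randomization has been determined". Section 3.4.1 requires "administration of at least 20 mL/kg IV/IO fluid resuscitation" and caps the amount at "40 mL/kg IV/IO crystalloid fluid prior to randomization". Section 1.4 expects more than 98% of comparable patients outside the study to start on NS.

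For the secondary cross-over outcome, section 5.2.1 adds crystalloid given before enrolment to the numerator and keeps the denominator within the intervention phase. Section 6.3.2 sets a limit of 25% in each arm. The same section sets criterion 1 for the primary endpoint: a difference of 65 points in mean NS share, with the lower 95% confidence limit above 60. Criterion 2 is also confined to study fluid within the study window.

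**The concern.** Compliance after randomization and total contrast in fluid type are different quantities, and section 2.1 asks about both. The primary ratio answers the first. It takes the same value whether a child reaches randomization with 20 or with 40 mL/kg of NS, so it says nothing about how far that fluid narrows the contrast between arms.

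The cross-over ratio does not fill the gap. Its numerator and denominator cover different periods, so it is neither a compliance rate nor a share of all fluid. It is also lopsided. Earlier NS counts as non-study fluid in the LR arm but not in the NS arm, so the LR arm can breach the 25% limit for reasons unrelated to what clinicians did after randomization.

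At stake is how the pilot is read. A large primary difference could be taken as the total exposure contrast, and a failed cross-over criterion as poor compliance.

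**Working it through.** The plan gives no figure for separation over all fluid. Its example for criterion 1 (section 6.3.2) is 90% against 25% NS, and 90 − 25 = 65 points, as intended for the intervention phase.

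**Inputs**
- Adherence after randomization (section 6.4, from the earlier diabetic ketoacidosis trial): 96% correct fluid in the NS arm and 91% in the intervention arm. Assume the other 9% in the LR arm is NS. The primary difference is 96 − 9 = 87 points.
- Pre-randomization volume P: 20 to 40 mL/kg (section 3.4.1), assumed equal in both arms and all NS.
- Total volume T: section 1.4 says that "children with sepsis often receive >100-200 mL/kg total crystalloid volume resuscitation within 24-48 hours". Take T = 100 and 200 mL/kg, including P. As a lower case take 80 mL/kg, since section 1.5 describes volumes up to and beyond that as common in the ED.
- One typical subject per arm, with adherence unrelated to volume.

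**Formulas**, with post-randomization volume V = T − P and NS share a after randomization:
- NS share over all fluid = (P + aV)/T.
- Arm difference over all fluid = 87 × V/T. An equal NS share of the earlier fluid in both arms cancels, so 98% in place of 100% changes nothing.
- Cross-over ratio in the LR arm, read literally = (P + 0.09V)/V.

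| P | T | V | NS arm | LR arm | Difference over all fluid | Primary difference | Cross-over ratio, LR arm |
|---|---|---|---|---|---|---|---|
| 20 | 100 | 80 | 96.8% | 27.2% | 69.6 | 87 | 34% |
| 40 | 100 | 60 | 97.6% | 45.4% | 52.2 | 87 | 76% |
| 20 | 200 | 180 | 96.4% | 18.1% | 78.3 | 87 | 20% |
| 40 | 200 | 160 | 96.8% | 27.2% | 69.6 | 87 | 34% |
| 20 | 80 | 60 | 97.0% | 31.75% | 65.25 | 87 | 42% |
| 40 | 80 | 40 | 98.0% | 54.5% | 43.5 | 87 | 109% |

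Section 6.3.2's example scales the same way. At T = 100 it becomes 65 × 80/100 = 52.0 points (P = 20) or 65 × 60/100 = 39.0 (P = 40). At T = 200 it becomes 58.5 or 52.0.

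**Cross-over ratio with perfect LR compliance.** The ratio reduces to P/V. With P = 40 and T = 100 it is 40/60 = 67%, although no NS was given after randomization. To stay within 25%, V must be at least 4P: 80 mL/kg when P = 20 and 160 mL/kg when P = 40.

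**The case against.** The strongest reply is that the primary ratio does its stated job. The first sentence of section 2.1 concerns compliance during the intervention phase. Section 3.1.2 defines the intervention as the fluid that remains after randomization, and section 3.2 calls compliance the primary feasibility assessment. This stands, and it is why the ratio should stay.

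A reader might infer that the protocol itself names the permitted 20 to 40 mL/kg as the danger, because section 9.6.3 speaks of "administration of a large volume of pre-study, non-randomized fluids that will prevent the necessary clinically important separation between study arms". That clause describes what would follow from extending the window beyond 15 minutes, and section 1.5 makes the parallel point about waiting for ICU admission. Both argue for early enrolment. The protocol answers that threat by enrolling in the ED, capping prior fluid, and not enrolling patients whose prior volume cannot readily be verified.

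Nor does the plan ignore earlier fluid. The cross-over outcome reacts to it strongly and has its own criterion, so in the less favourable scenarios a pre-specified secondary criterion would fail. That shows sensitivity to the fluid, but it does not make the ratio interpretable, and the criterion plays no part in the primary decision.

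Finally, the sizes depend on an assumed total. Section 1.4's range refers to resuscitation volume, whereas the primary denominator also counts maintenance fluid, which would reduce the dilution. This also stands.

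**Conclusion.** The point holds as a modest improvement to the plan. The primary ratio is sound for compliance, but no pre-specified measure gives the total difference in fluid type between arms. Under the stated assumptions that difference is 52 to 78 points for totals of 100 to 200 mL/kg, against 87 on the primary ratio, and 43.5 to 65.25 at a total of 80 mL/kg. The clearer defect is the cross-over ratio: as written it can exceed 100% and can fail under perfect LR compliance.

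Two further inferences are not supported. One is that the plan misses its own 65-point mark. That mark is defined for the intervention phase, where the planning difference is 87; even if borrowed for all fluid, three of the four scenarios at 100 to 200 mL/kg exceed it. The other is that the main trial's effect size would be set wrongly. Nothing in the documents says the pilot's separation figure will set it. The only effect discussed, a 1 to 2% absolute mortality reduction in section 1.1, is tied to earlier adult studies.

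**What to change.** Keep the primary ratio and both of its criteria for compliance. Pre-specify one supplementary estimate: each subject's NS share from the first recorded crystalloid to the end of the study window, with pre-randomization volume in numerator and denominator. Report the arm difference with the same bias-corrected bootstrap interval as in section 6.3.2, and attach no pass mark.

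Redefine the cross-over ratio so that both parts cover the same period. Dropping pre-enrolment fluid from the numerator would make it a pure compliance measure, and the supplementary estimate would carry the rest. State the numerator window of the primary ratio in section 5.2.1 so that it matches section 6.1.

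No new data are needed: section 4.4 records prior crystalloid, and section 5.1.1 records the time and volume of study and non-study fluids. The costs are one more analysis, a less favourable separation figure, and incomplete volumes for some transferred patients, whose number should be reported.
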